9.4.2 Secondary outcomes

Secondary outcomes will consist of four implementation outcomes drawn from the Consolidated Framework of Implementation Research (CFIR) and related work by Proctor et al.³⁹⁻⁴¹ Acceptability will be operationalized as the percent of study participants who are retained in each group over time (that is, continue to engage with the care coordinators when contacted). Appropriateness will be operationalized as: a) the types of problems with care coordination uncovered in response to the survey in the intervention group, and b) the frequency of different types of care coordinator activities in each group (i.e., facilitating provider-provider communication, facilitating transportation, etc.). Fidelity will be measured by tracking the percent of eligible individuals who receive care coordination services. Implementation Cost (or Efficiency) will be measured as the total number of care coordinator hours spent in each group. Implementation outcomes will be measured through manual review of the EHR, using a structured abstraction tool.

9.5 Data Analyses

We will compare the characteristics of the PLWD in each study group, using chi-squared tests for dichotomous variables and t-tests for continuous variables, to confirm that the study groups are balanced ($p > 0.05$). We will use Poisson regression to compare study groups for the outcome of the number of events (ED visits or hospital admissions) per person-time alive, adjusting for care management team (as it was used to stratify randomization⁴²) and any co-variates that were imbalanced between the study groups at baseline. We will conduct analyses using an intention-to-treat approach, considering all individuals as members of the group to which they were randomized. We will use descriptive statistics to report implementation outcomes.

We will take biological sex and race/ethnicity into consideration in both the design and valid analysis of the trial. We will employ inclusive eligibility criteria, including individuals in the study regardless of sex or race/ethnicity. We will allocate study participants of both sexes and all races/ethnicities to the intervention and control groups by the unbiased process of randomization. We will conduct unbiased assessment of the occurrence of outcomes in all study participants. We will also use unbiased methods of statistical analysis and inference for the study population overall. In addition, we will conduct analyses to determine if the effect of the intervention varies with subgroups by sex and, separately, by race/ethnicity. For Aim 1 (which has the combined outcome of emergency department visits or hospital admissions), we will conduct exploratory moderator analyses with sex and race as potential moderators of treatment effect by introducing moderator x treatment interactions into our regression models. For Aim 2 (which captures implementation outcomes), we will conduct exploratory analyses stratifying implementation outcomes (such as the types and frequencies of care coordination activities provided) by sex and, separately by race/ethnicity.

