Individuals with qualifying events in both groups will receive care coordination services, which will be consistent with the professional standards of the American Case Management Association and the Case Management Society of America.^{29,30} Usual care includes describing care coordination to the patient or proxy and inviting them to engage in care coordination; approximately 70-80% of people agree to engage. Each interaction with a patient or proxy (including declining care coordination) is documented in the electronic health record (EHR). Usual care coordination is broad and encompasses post-discharge medication reconciliation, inquiries about any symptoms post-discharge, a review of upcoming appointments, assistance with obtaining transportation, review of paid home care services, and any other needs that may arise, with the primary goal of preventing rehospitalization. Patients and proxies are given the care coordinator’s contact information and are invited to reach out with any questions or concerns. Care coordination in the intervention group will start narrowly, with the care coordinator seeking to understand the positive screening result (exactly what the patient or proxy thinks is not working well and why). The care coordinator will then seek to address the issue, documenting the process in the EHR. The care coordinators will be free to engage in broader care coordination activities (e.g., general medication reconciliation, reviewing upcoming appointments, arranging transportation, etc.) at their discretion.

The length and frequency of interactions between the patient or proxy and the care coordinator varies depending on the patient’s needs and the care coordinator’s discretion. Patients are followed for a minimum of 30 days and a maximum of 1 year, which is a typical duration for care coordination.³¹ Care coordination starts at the time of the qualifying event. Follow-up for ED visits and hospitalizations begins after the first 30 days of care coordination.

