- (ii) Research could not practicably be conducted without the waiver: The research could not practicably be carried out without the waiver because, during usual care, patients are not aware of care coordinator resources unless they are assigned a care coordinator through a physician referral or after a recent discharge. If we

were to try to obtain authorization, we would need to explain care coordination, which may then raise concerns about care coordination among the participants and proxies. This would be especially problematic in the control group, which by the design of the study cannot directly request the assistance of care coordinators. This would then create problems for the feasibility and validity of the trial.

- (iii) Research could not practically be conducted without access to and use of PHI: The research could not practically be carried out without the use of identifiable information. The trial relies on identifying community-dwelling Medicare beneficiaries 65 years and older with dementia who are attributed to New York Quality Care. We then need to reach out to those individuals who qualify for care coordination in each group, provide care coordination services, review their electronic health record data for implementation outcomes, and follow them over time for the occurrence of emergency department visits and hospital admissions as captured in claims. This study is not possible without the use of identifiers.

If this waiver is granted, then there will be no recruitment or enrollment *per se*, because we will include 100% of eligible individuals. Even with a waiver of informed consent, participants in both the intervention and control groups will be able to decline care coordination services if they do not want them. Currently, with usual care, about 70-80% of Medicare beneficiaries who are approached by the NYQC care coordinator agree to engage in care coordination. Each interaction with a patient or proxy (including declining care coordination) is documented in the EHR.

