9.2 Sample Size and Randomization

The primary outcome is the number of events (emergency department visits or hospitalizations) / person-time alive. Preliminary data (for the control group) show an average event rate per person of 1.99 events over 334 live days (0.92 years). Using Poisson regression, with a sample size of 688 PLWD and assuming 20% attrition and $\alpha = 0.05$, we have >90% power to find an event rate ratio of 0.74 (i.e., a reduced event rate of 1.47 or lower in the intervention group vs. 1.99 in the control group), which is a meaningful difference. Data will be analyzed using an intention-to-treat approach. We will use descriptive statistics to report our secondary implementation outcomes; these are designed to inform future iterations and dissemination of this intervention, rather than test hypotheses per se.

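### The primary Poisson analysis of repeated ED visits and admissions makes no provision for overdispersion; default standard errors would overstate precision, and the stated power holds only to a variance/mean of about 2

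*Combined protocol and SAP*

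**What the plan says.** Section 9.2 defines a repeated-event outcome: "The primary outcome is the number of events (emergency department visits or hospitalizations) / person-time alive". The planning value is a mean only: "Preliminary data (for the control group) show an average event rate per person of 1.99 events over 334 live days". From this, using Poisson regression with 688 people, 20% attrition and alpha 0.05, the plan concludes that "we have >90% power to find an event rate ratio of 0.74", that is, "a reduced event rate of 1.47 or lower in the intervention group vs. 1.99 in the control group".

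Section 9.5 gives the primary analysis: "We will use Poisson regression to compare study groups for the outcome of the number of events" per person-time alive, adjusted for care management team and for any covariates found imbalanced at baseline, by intention to treat.

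Neither section, nor any other part of the document, mentions a robust variance, a scale parameter, a negative binomial model, a check of dispersion or a fallback model. No SD or variance of the event count is reported. Section 9.5 also promises unbiased methods of analysis and inference, but this names no variance method.

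**The concern.** Default Poisson standard errors are valid only if the variance equals the mean, given the covariates and person-time in the model. For repeated acute events that is unlikely to hold exactly. The document itself points to clustering within people and to differences in risk between them. Section 3 describes usual care coordination as carried out "with the primary goal of preventing rehospitalization", which treats a second admission after a first as a real risk. Section 4.3 keeps people with severe dementia in the study alongside milder cases. The document also does not say whether an ED visit that ends in admission counts as one event or two; counting two would add to the variance.

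Care management team and the other covariates may absorb part of the between-person variation. Whatever remains makes the model-based interval too narrow, by a factor of the square root of phi on the log scale.

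Two things are at stake. A modest benefit could be declared significant when the data do not support it. And the stated power could be too high in a trial whose size is in effect fixed: there is no further recruitment, "because we will include 100% of eligible individuals" (Section 4.3).

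**Working it through.** **Inputs.** From Section 9.2: control mean 1.99 and intervention mean 1.47 events per person, 20% attrition, alpha 0.05. From Section 3: 344 per arm. Analysed per arm: 344 × 0.8 ≈ 275. Sidedness is not stated; two-sided is assumed. Phi is the residual variance/mean. It is not in the documents, so it is an assumption shown from 1 to 5.

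**Step 1: the plan's own figure.** Expected events are 275 × 1.99 = 547.25 and 275 × 1.47 = 404.25. The standard error of the log rate ratio at phi 1 is √(1/547.25 + 1/404.25) = 0.0656. The log ratio is ln(1.47/1.99) = −0.3029. Power = Φ(0.3029/0.0656 − 1.96) = Φ(2.66) = 99.6%. The claim of more than 90% is therefore correct under pure Poisson variance.

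**Step 2: allowing for overdispersion.** With a valid variance the standard error becomes 0.0656 × √phi, and power = Φ(0.3029/(0.0656√phi) − 1.96). If the model-based standard error is kept, the true two-sided type I error is 2 × (1 − Φ(1.96/√phi)).

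| phi | Type I error, model-based SE | Power, valid variance |
|---|---|---|
| 1 | 5% | 99.6% |
| 1.5 | 11% | 96.5% |
| 2 | 17% | 90.4% |
| 3 | 26% | 76.0% |
| 5 | 38% | 54.2% |

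Power falls to 90% at phi 2.03 (2.01 if the ratio is taken as exactly 0.74) and to 80% at phi 2.72. With a gamma spread of underlying rates, phi = 1 + 1.99 × CV², so phi 2 in the control arm needs a between-person coefficient of variation of √(1/1.99) ≈ 0.71.

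**Step 3: effect on the primary conclusion.** An observed ratio r is just significant when −ln(r) = 1.96 × √(phi/547.25 × (1 + 1/r)). This gives r = 0.885 at phi 1, 0.839 at phi 2, 0.805 at phi 3 and 0.751 at phi 5. At phi 3, observed ratios between about 0.80 and 0.88 would be called significant by plain Poisson but not with a correct variance.

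- Observed ratio 0.84: plain Poisson gives 95% CI 0.74 to 0.95, p = 0.006. At phi 3 the correct result is 0.68 to 1.04, p = 0.11.
- Observed ratio 0.74: at phi 5 the correct 95% CI is 0.56 to 0.99, so it remains significant.

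**Step 4: simulation.** Gamma-frailty counts were generated with 275 per arm, and a log person-time offset was used. Two inputs are not in the documents and were assumed: two care teams with rates 10% below and 10% above average, fitted as a covariate, and follow-up cut by death at 0.18 per year. There were 6,000 null and 4,000 alternative replicates per phi.

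| phi | Type I error, plain Poisson | Type I error, robust | Power, robust |
|---|---|---|---|
| 1.5 | 10.9% | 4.8% | 97.3% |
| 2 | 17.8% | 5.0% | 91.9% |
| 3 | 26.9% | 5.1% | 79.4% |
| 5 | 39.2% | 5.5% | 57.6% |

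Simulated power is slightly above the formula because gamma frailty gives a lower phi in the arm with the lower rate.

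**The case against.** Naming Poisson regression does not commit the team to model-based standard errors. The remedy proposed here is also Poisson regression, so an analyst who used a sandwich variance would still be following the text. That is true, and it is why the harm is stated as conditional. But the default in that case is model-based, and an unmasked trial should not leave open a choice that can decide significance.

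The size of the harm is assumed. The documents give no variance, and nothing in them supports phi 3 or 5 in particular; at phi 1.5 power is still 96.5%. This stands. The omission is certain, but the magnitude is not. Likewise, the reference to preventing rehospitalization states a goal of care and gives no frequency, so it makes clustering plausible without measuring it.

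The limit of about 2 treats attrition as complete loss of 20% of people. The outcome is measured in claims per person-time alive, and Section 6.1 says everyone contributes data, so partial follow-up could count. With all 344 per arm the limit is 2.54, and power is 95.5% at phi 2 and 84.7% at phi 3. That is a fair upper bound, but 275 per arm follows the plan's own assumption.

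Finally, the power figure is not an arithmetic error, and the document does not show which variance was used. Only the naming of Poisson regression suggests variance equal to the mean.

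**Conclusion.** The concern holds. The primary analysis and its power statement name Poisson regression for a repeated-event count and make no provision for variance above the mean. If the model is run with default standard errors and phi exceeds 1, the primary interval and p-value will be too optimistic: a nominal 5% test has a true level of 11% at phi 1.5, 17% at phi 2 and 26% at phi 3. The power claim survives up to phi of about 2.0 under the plan's 20% attrition, or about 2.5 with no loss at all. These figures rest on a two-sided 5% test, the Section 9.2 means taken per person, and an assumed phi. The rate ratio itself is not biased by overdispersion, and a strong effect near 0.74 would survive correction; a modest one might not. This should be fixed before analysis.

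**What to change.** In Section 9.5, specify Poisson regression with a log person-time offset and robust (sandwich) variance, adjusted for care management team, as the basis for the primary p-value and 95% CI. Name negative binomial regression as a sensitivity analysis. A negative binomial or quasi-Poisson primary model would also close the gap; what matters is that one is fixed in advance.

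In Section 9.2, report the variance of the event count in the preliminary data and restate power with it. If person-level counts are not available, show power over a range of phi.

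The cost is a change of wording and one re-run of the power calculation, with the same outcome, data and software. The downside is wider intervals if overdispersion is present, and possibly a stated power below 90% that cannot readily be recovered by adding participants.

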4.1 Inclusion Criteria

Participants must meet all of the inclusion criteria to participate in this study.

- Medicare beneficiaries ≥65 years old who are attributed to NYQC by Medicare,²⁴
- Who have dementia, using the previously validated Bynum-Standard 1-year definition with ICD-10 codes from Medicare claims for the previous 12 months,^{25,26} and

- Who had fragmented ambulatory care, based on Medicare claims in the previous 12 months, defined as a reversed Bice-Boxerman Index (BBI) score $\geq 50^{\text{th}}$ percentile.
^{27,28}

$$\text{reversed BBI} = 1 - \text{BBI} = 1 - \frac{(\sum_{i=1}^p n_i^2) - n}{n(n-1)}$$

where n = total number of ambulatory visits in the 12-month period

n_i = number of ambulatory visits to provider i

p = total number of ambulatory providers

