6 STUDY PROCEDURES

6.1 Schedule of Evaluations

This trial does not have a schedule of evaluations per se. Instead, we show a timeline of events for all participants in the trial (Figure 3).

Figure 3. Timeline of events for each participant (not to scale)

*See section 3 for the definition of qualifying event, which varies based on the arm of the trial

†Care coordination may extend beyond 30 days for participants in either trial arm, at the discretion of the care coordinator, but the follow-up period still starts after the initial 30 days of care coordination. For those participants who do not have a qualifying event, their follow-up period for ED visits or hospitalizations will start 4 months after randomization (simulating the 3-month qualifying period + 1 month during which they did not receive care coordination). See also section 5.1 for more information.

The study will use three data sources: the survey on perceptions of care coordination, the EHR, and Medicare claims. The survey data will be used to determine eligibility for care coordination in the intervention group. The EHR will be used to collect demographic and clinical characteristics of patients (age, race, sex, co-morbidities), as well as the implementation outcomes. Medicare claims will be used to measure fragmentation as an eligibility criterion and the primary outcome of ED visit or hospital admission over 12 months. The survey will be administered by care coordinators, the EHR data collection will be done by a research assistant, and the Medicare claims will be analyzed by data analysts.

Note that all participants will contribute data to the study whether they are selected for care coordination or not. This is because we are comparing two methods for allocating care coordinators, and we are interested in ED and hospitalization outcomes for both those selected and those not selected.

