6.2.2 Enrollment, Baseline, and/or Randomization

Enrollment

The enrollment date for all participants will be the date of randomization.

Baseline Assessments

The research assistant will manually review the EHR for participants' demographic characteristics (age, race, sex, co-morbidities).

Randomization

See section 6.1 for a timeline of randomization, intervention, and follow-up.

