9 STATISTICAL CONSIDERATIONS

9.1 General Design Issues

The trial is based on the hypothesis that assigning care coordinators to PLWD whose care partners' perceive a problem with care coordination will result in fewer ED visits and hospitalizations than assigning care coordinators to PLWD at the time of hospital

discharge. To avoid circularity, we will separate exposures and outcomes in time. That is, we will have a 3-month exposure period, during which a hospitalization that prompts care coordination will only be counted for the exposure and not as an outcome.

The 3-month time period was chosen, based on preliminary data suggesting that more fragmented care over 12 months independently increases the risk of an incident ED visit^(under review) or incident hospital admission²¹ in the subsequent 1-3 months, compared to less fragmented care.

A parallel design was chosen because it is a robust design that allows for concurrent comparisons. The outcome of ED visit or hospitalization will be measured using Medicare claims data, which are the gold standard, because they capture events across health systems and are thus broader than EHRs.

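### Baseline significance tests choose every covariate in the primary model except care management team, and prior ED and hospital use is not among the named baseline variables, so available precision is given up

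*Combined protocol and SAP*

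**What the plan says.** Section 9.5 (Data Analyses) compares baseline characteristics by chi-squared and t-tests "to confirm that the study groups are balanced", with p > 0.05 as the criterion. The primary Poisson model is then fitted "adjusting for care management team", because team stratified the randomisation, and also for "any co-variates that were imbalanced between the study groups at baseline". No other covariate is fixed in advance.

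The baseline variables are named in Section 6.2.2, where the research assistant abstracts from the EHR the "demographic characteristics (age, race, sex, co-morbidities". Section 6.1 gives the same list. Neither section mentions earlier ED visits or admissions, and nor does any other.

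The data for such a variable are already in use. Section 4.1 requires that participants "had fragmented ambulatory care, based on Medicare claims in the previous 12 months". Section 6.1 adds that "Medicare claims will be used to measure fragmentation as an eligibility criterion and the primary outcome of ED visit or hospital admission". Section 9.1 prefers claims for these events because "they capture events across health systems and are thus broader than EHRs".

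**The concern.** Randomisation makes any baseline difference a matter of chance, so a p-value below 0.05 says nothing about whether a variable predicts ED visits or admissions. Precision comes from adjusting for variables that predict the outcome, whether or not they happen to be imbalanced. The rule therefore selects on the wrong property. It also leaves the primary model unknown until the baseline tests are run: with four independent tests, the chance that at least one variable enters is 1 − 0.95⁴ = 19%.

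The omitted variable is the outcome measure itself, one year earlier. If some people use the ED and hospital persistently more than others, chance differences between the arms in prior use stay in the estimate as noise. Recruitment cannot make up that loss, because Section 4.3 says "we will include 100% of eligible individuals".

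Validity is not at stake. The unadjusted estimate is unbiased on average, the rule looks only at baseline data, and a robust test keeps its nominal size.

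**Working it through.** **The plan's own figure (Section 9.2).** Inputs: 688 randomised, 20% attrition, so 275 per arm; 1.99 and 1.47 events per person; α = 0.05, taken as two-sided. Under pure Poisson variation:

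- SE of the log rate ratio = √[(1/1.99 + 1/1.47)/275] = √(1.1828/275) = 0.0656.
- |ln(1.47/1.99)| = 0.3029.
- Power = Φ(0.3029/0.0656 − 1.96) = 99.6%.

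The stated >90% is met. In this model people do not differ in underlying rate, so prior use could explain nothing.

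**Allowing people to differ.** Let k be the variance of a person-level multiplier with mean 1. Then Var = (1/1.99 + 1/1.47 + 2k)/275, and variance/mean = 1 + 1.99k in the control arm. The documents do not give k. Unadjusted power for an assumed variance/mean of 2 to 4:

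| Variance/mean | k | SE | Power |
|---|---|---|---|
| 2 | 0.50 | 0.0892 | 0.92 |
| 3 | 1.01 | 0.1078 | 0.80 |
| 4 | 1.51 | 0.1236 | 0.69 |

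**Effect of always adjusting.** This was simulated with gamma-Poisson counts, 275 per arm and 4,000 trials per setting. The mean is 1.99 in control follow-up and, by assumption, in the prior year. The assumed correlation between prior and follow-up counts is r. Poisson models were fitted with and without log(1 + prior count), using robust standard errors. Monte Carlo error is about 0.006 on power and 0.015 on variance reduction.

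| r | Variance reduction (variance/mean 2 to 4) | Power at variance/mean 3, ratio 0.74 |
|---|---|---|
| 0.25 | 4.9% to 6.1% | 0.801 → 0.825 |
| 0.40 | 13.2% to 17.0% | 0.802 → 0.866 |
| 0.50 | 21.9% to 24.3% | 0.798 → 0.892 |
| 0.60 (variance/mean 3 and 4 only) | 32.9% to 35.4% | 0.807 → 0.933 |

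Multiplying the formula variance by (1 − reduction) carries this to the ends of the range:

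- Variance/mean 2, r 0.25 (5%): SE = 0.0892 × √0.95 = 0.0869; power 0.92 → 0.94.
- Variance/mean 4, r 0.50 (23%): SE = 0.1236 × √0.77 = 0.1084; power 0.69 → 0.80.

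In participants, a 23% reduction is worth 550/(1 − 0.23) − 550 = 164 more on the 550 analysed.

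**A different model.** Log-normal multipliers with k = 1 and correlation 0.7 between the two years' multipliers (2,000 trials) gave power of 79.8% never adjusting, 80.8% adjusting only if p < 0.05, and 86.4% always adjusting. With correlation 0.5 the figures were 79.8%, 80.3% and 83.2%.

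**Adding prior use only to the tested list.** The noise that adjustment removes is proportional to z², the squared standardised imbalance. Always adjusting removes E[z²] = 1 unit. The 0.05 rule acts in about 5% of trials and removes E[z²; |z| > 1.96] = 2(1.96 × 0.0584 + 0.025) = 0.279. At r 0.5 the simulated reduction was about 7%, against about 23% for always adjusting.

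**Standard errors.** Under the null at variance/mean 3 and r 0.5, plain Poisson errors reject in 25.8% of trials unadjusted and 19.5% adjusted. Robust errors reject in 4.8% and 5.2%.

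**The case against.** The best case for leaving the plan alone is that nothing in it is invalid and that the gain rests on quantities the documents do not supply. On Section 9.2's own Poisson inputs the gain is nil. At variance/mean 2, power is already about 0.92 without prior use. The higher correlations are demanding. In the gamma-Poisson model r cannot exceed (v − 1)/v, where v is variance/mean. At v = 2 an r of 0.5 would need perfectly stable individual risk, and at v = 3 it needs a correlation of 0.75 between the two years' underlying rates. Follow-up also starts up to 4 months after randomisation, which may weaken the link. All of this stands as a limit on size. It does not defend the rule: some gain appears at every setting with between-person variation, and no setting favours selection by p-value.

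Three smaller points. The simulation drops 20% of participants and gives the rest equal exposure, whereas the outcome is counted per person-time alive. This shifts absolute power, but the formula's proportional variance reduction does not depend on the number analysed. The gain was shown only for the prior-use count, not for age, sex or co-morbidity. The clause on imbalance does not repeat p > 0.05, but no other definition of balance is given.

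The inflated type I error of plain Poisson errors is a separate problem, which adjustment does not repair.

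**Conclusion.** The concern holds as a matter of efficiency and prespecification. Apart from care management team, the primary model's covariates are chosen by tests that cannot identify prognostic variables, and the most obvious prognostic variable is not named. Under the assumed ranges (variance/mean 2 to 4, r 0.25 to 0.6), always adjusting for prior use cuts the variance of the log rate ratio by about 5% to 34%. At mid-range overdispersion that is roughly 2 to 13 points of power. If people barely differ in underlying rate the gain vanishes, though that is unlikely for repeated ED visits and admissions. The gain is valid only with standard errors that allow for overdispersion. The change should be made; the trial is not invalid without it.

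**What to change.** In Section 9.5, delete the balance tests and the adjustment they trigger, and report baseline characteristics descriptively. Before randomisation, fix the primary model's covariates as:

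- care management team;
- log(1 + number of ED visits and admissions in Medicare claims in the 12 months before randomisation);
- age;
- sex;
- one co-morbidity measure: a count over a list of EHR-abstracted conditions fixed in advance, with a stated rule for conditions not recorded.

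State that standard errors allow for overdispersion, through robust sandwich errors or a negative binomial model. Add the prior-use count to the baseline variables in Sections 6.1 and 6.2.2. Race can remain in the exploratory moderator analyses already planned.

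The cost is SAP wording, one variable derived from claims the ACO already manages, a short agreed list of conditions, and a few degrees of freedom. Sample, procedures and care do not change.
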